Available small studies, case reports (14-22), and our preliminary data (87) support that DDN likely produces neural plasticity at both spinal and supraspinal levels. Thus, our central hypothesis is that ***DDN at MTrP induces plasticity in the spinal and supraspinal pathways and produces therapeutic effects.*** While the steady increase in therapeutic use of DDN implies its clinical potential, its optimal use is yet to be established, largely due to the limited mechanistic understanding of its neurophysiological effects. This pilot project is our first step towards understanding the neurophysiological mechanisms of DDN, specifically the spinal mechanisms of DDN-induced plasticity. This project evaluates these mechanisms via two specific aims:

Aim 1. To evaluate the effects of DDN on proprioceptive reflexes in people with spasticity due to stroke.

In people with spasticity the excitability of the H-reflex pathway (an electrical analog of spinal stretch reflex) becomes elevated and reciprocal inhibition of the plantarflexors by the dorsiflexors becomes impaired (25, 26). Thus, to investigate the effects of DDN at the medial gastrocnemius (MG) MTrP on excitatory and inhibitory proprioceptive reflexes, in 20 individuals with spasticity due to stroke we will measure the H-reflex – M-wave (H/M) recruitment curves and reciprocal inhibition in the triceps surae muscles before, immediately after, 90 minutes after, 24 hours after, and 72 hours after DDN. One week prior to DDN, the same measurements will be repeated 5 times, with inter-measurement intervals matching to pre and post DDN measurements. We anticipate that decreases in H-reflex size and reciprocal inhibition will occur between pre and post DDN time points.

Aim 2. To evaluate the effects of DDN on cutaneous reflexes in people with spasticity due to stroke. Modulation of cutaneous reflexes to non-noxious stimulation of the skin become abnormal

post-stroke, reflecting the altered somatosensory processing in this population (33, 34). Thus, in this project, we will examine cutaneous reflex responses to non-noxious stimulation of the distal limb (i.e., at or below the area treated with dry-needling) at the same time points as the proprioceptive reflexes before and after a single DDN session. We anticipate that cutaneous reflex amplitudes will be decreased after DDN.

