Additionally, to interpret these reflex changes related to typical clinical measures, we will measure passive and active dorsiflexion range of motion (ROM) and the Modified Ashworth scale, Fugl-Meyer, and 10-m walk test. These measurements will facilitate the development of future DDN clinical trials towards establishing spinal neurophysiological mechanisms of DDN.

The findings from this project would also help clinicians estimate when post DDN motor practice/training therapies should be administered for improving motor function in persons with and without spasticity. The data obtained through this pilot project will significantly strengthen our future NIH R-series applications, through which we plan to test the hypothesis that a single administration of DDN procedures will produce lasting effects on spinal neurophysiology that support temporary relief/alleviation of sensorimotor impairments in people with spasticity due to chronic stroke.

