9.0 Study Design / Methods

This study is a partial cross-over waitlist control design, in which each of the 20 participants post stroke will participate in 7 visits over a two-week period, during which measurements will be taken 10 times. Neurophysiological and functional measurements will be collected five times over 3 visits during the first week (treatment as usual control week), through which each participant will serve as their own "controls" for their second week of measurements. No sham or other treatment procedure will occur during this week. On the second week, all participants will transition to the DDN intervention week where five measurements will be collected over 3 visits (one pre-DDN baseline and four post-DDN measurements: immediately after, 90 minutes, 24 hours, and 72 hours).

Deep Dry Needling (DDN)

DDN procedures used in this project have been widely used in clinical practice to treat spasticity and pain in individuals with neurological and non-neurological (orthopedic) injuries [15,16,18,20,21,48,75].

Each participant receives a single session of DDN, targeting the medial gastrocnemius. In each DDN session, first, localized hypersensitive spots in palpable taut bands of the targeted skeletal muscles (i.e., MTrPs)(75, 76) are identified with pincer palpation. Then, after cleaning the skin area over a MTrPs with alcohol swabs, a disposable stainless steel acupuncture needle is inserted into the skin, penetrating approximately 15 to 20 mm to the depth of the trigger point, until the local twitch response (LTR) is elicited. Once the LTR is confirmed, the needle is moved up and down

(~4-5 mm vertically) with a small piston motions (approximately at 1 Hz for 25 to 30 seconds) with no rotation at the MTrPs (9,10, 38). The same procedure is repeated at other MTrPs in the same local skin region as needed until the LTR is eradicated. After removing the needle, the needled area is rubbed to prevent bleeding and bruising. Each participant will complete 5 repetitions of each of the following: ankle plantarflexion/dorsiflexion passive range of motion (PROM), sub-maximal concentric and eccentric contractions of the plantarflexors as would be typical in a clinical setting.

Electromyography (EMG) and nerve stimulation

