At the beginning of each session, surface self-adhesive Ag-AgCl electrodes are placed over the TA, medial and lateral gastrocnemius (MG and LG), and soleus muscles of the studied leg. Throughout the study, all EMG activity is amplified, band-pass filtered (10-1000 Hz), sampled at 3,200 Hz, and stored. Nerve stimulation protocol consists of 4 components: (1) single pulse posterior tibial nerve stimulation for the triceps surae H-reflex / M-wave (H/M) recruitment curve measurement, (2) single pulse common peroneal (CP) nerve stimulation for the TA H/M recruitment curve measurement, (3) multiple pulse (train) tibial nerve stimulation for cutaneous reflex measurement, and (4) multiple pulse (train) superficial peroneal (SP) nerve stimulation for cutaneous reflex measurement.

- (1) ***Single pulse posterior tibial nerve stimulation for triceps surae H/M recruitment curve:*** To elicit the triceps H-reflex, the tibial nerve is stimulated in the popliteal fossa, using surface Ag-AgCl electrodes and isolated constant current stimulation. The stimulating electrode pair is placed so as to minimize the H-reflex threshold and to avoid stimulation of other nerves. For eliciting the H-reflex and M-wave, a 1-ms square stimulus pulse is delivered when the participant has maintained his/her natural standing level (typically, 10-20% of maximum voluntary contraction (MVC) level of EMG activity) of soleus EMG activity for at least 2 s. The minimum interstimulus interval is 5 s. An H/M recruitment curve is obtained by gradually increasing the stimulus intensity in increments of 1.2-2.5 mA from the H-reflex threshold to the maximum H-reflex (H_{max}) to an intensity just above what is needed to elicit the maximum M-wave (M_{max}) [77-79], while the participant stands and maintains the above noted level of soleus EMG activity. About 10 different intensities are used to obtain a recruitment curve, and four EMG responses are averaged to measure the H-reflex and M-wave at each intensity. Then, about 100 responses are elicited at the H_{max} level of stimulus intensity (i.e., weak to mild intensity) while monitoring cortical electroencephalographic (EEG) activity.

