10.0 Data Management

Data analysis: Reflex sizes are calculated in reference to each participant's M_{max} measured during natural standing. For example, the peak-to-peak H-reflex amplitude is normalized to the peak-to-peak M_{max} amplitude, and the mean rectified H-reflex amplitude is normalized to the mean rectified M_{max} amplitude.

For comparing reflex sizes before and after dry needling, a two-way repeated measures ANOVA (studied side of the extremity \times time) will be used, together with Student t-test with Bonferroni correction as a post-hoc test. For simple comparison between participants without known neurological conditions and participants after stroke (e.g., age and M_{max}), and assessments of changes in sensory and motor function (i.e., only applicable to participants after stroke), a Student t-test will be used.

Data management: The data will be managed by the PIs and research coordinator at the College of Health Professions (CHP). All EMG and assessment data are electronically stored in the secure CHP server with password protection. Only the investigators directly involved in this project have access to these data.

Protection of participant confidentiality is essential in human clinical trials. The participants' confidential information will be securely stored in locked cabinets of a locked room and a password-protected computer, and only the principal and co-investigators and the research coordinator will have access to the participant's confidential information. For the length of the study, limited personal information (specifically, the participant's name, address, and social security number) will also be accessible to the program administrator for processing the participant reimbursement paperwork. Investigators and therapists, who run data collection sessions, will have access to the EMG and other collected data for the purpose of analysis, but will have no access to the participant's confidential information. Alphanumeric codes will be assigned to each participant's dataset to protect confidentiality.

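### The functional-change t-test names no contrast, and no stated analysis uses the untreated control week that was built in for comparison

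*Combined protocol and SAP*

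**What the plan says.** Section 9.0 (Study Design / Methods) describes the first week as follows: "Neurophysiological and functional measurements will be collected five times over 3 visits during the first week (treatment as usual control week"). Its purpose is that participants act as their own controls "for their second week of measurements". On treatment in that week it says "No sham or other treatment procedure will occur during this week". The DDN week has one measurement before needling and four after it (immediately, 90 minutes, 24 hours, 72 hours). Everyone has the control week first.

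Section 1.0, Aim 1, says the control-week measurements are made "with inter-measurement intervals matching to pre and post DDN measurements". That is stated for the reflex measures, but Section 9.0 gives the functional measures the same five control-week occasions.

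Section 10.0 (Data analysis) holds the only analysis text. On function: "assessments of changes in sensory and motor function (i.e., only applicable to participants after stroke), a Student t-test will be used". On reflexes: "For comparing reflex sizes before and after dry needling, a two-way repeated measures ANOVA", with side of the limb and time as the factors and Bonferroni-corrected t-tests afterwards.

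Section 1.0 gives the role of the functional measures: "to interpret these reflex changes related to typical clinical measures", and to help develop later DDN trials.

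**The concern.** The design pays for a control week, and the analysis text never says how it is used. With ten measurement occasions per participant, a t-test on change could mean at least three things: DDN-week post against pre, post values in week 2 against post values in week 1, or change in week 2 against change in week 1. Each answers a different question, and an unnamed choice can be made after the data are seen.

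The reflex sentence beside it is framed as before against after needling and has no week factor. If the functional test is read the same way, it is a pre/post test inside the DDN week. Any change over those days that would have occurred without needling is then counted as a DDN effect. It could be carried into the interpretation of the reflex results and the planning of later trials.

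**Working it through.** **No figure to reproduce.** The documents give no effect size, SD, significance level or drift for the functional outcomes. N = 20 is stated in Section 5.0. Everything else here is assumed.

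**Assumptions.** Two-sided 0.05; n = 20 complete pairs; approximately normal change scores with the same SD in both weeks. Drift (change without needling, taken in the direction of improvement) is d1 in the control week and d2 in the DDN week, in SDs of the change score. The correlation r between the two weeks' changes is 0, 0.3 or 0.5.

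**Two candidate tests.**
- Pre/post in the DDN week: standardised shift = d2 + DDN effect.
- D = (DDN-week post minus pre) minus (control-week change at the matching time point). SD of D = √(2(1 − r)) = 1.414 / 1.183 / 1.000. Standardised shift = (d2 + DDN effect − d1) / √(2(1 − r)).

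Rejection probabilities come from the noncentral t with 19 df, critical value 2.093 and noncentrality = shift × √20.

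**No DDN effect, equal drift in both weeks**

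| Drift (SD) | Pre/post rejects | D rejects |
|---|---|---|
| 0 | 5.0% | 5.0% |
| 0.2 | 13.6% | 5.0% |
| 0.3 | 24.7% | 5.0% |
| 0.5 | 56.5% | 5.0% |

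**No DDN effect, drift smaller in week 2** (D at r = 0 / 0.3 / 0.5)

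| d1, then d2 | Pre/post rejects | D rejects |
|---|---|---|
| 0.3, 0.15 | 9.8% (9.3% favouring DDN) | 7.4 / 8.4 / 9.8% (under 1% favouring DDN) |
| 0.3, 0 | 5.0% | 14.7 / 19.0 / 24.7%, nearly all against DDN |
| 0.5, 0 | 5.0% | 32 / 43 / 56%, nearly all against DDN |

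**Break-even.** The two tests have the same error rate when d2 = (d1 − d2) / √(2(1 − r)), that is d2/d1 = 1 / (1 + √(2(1 − r))) = 0.41 / 0.46 / 0.50. D has the lower error rate above that ratio; pre/post has it below.

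**Power for a true DDN effect of 0.66 SD**, the size that gives pre/post about 80% at n = 20 without drift (D at r = 0 / 0.3 / 0.5):
- Equal drift: D shift = 0.66/1.414 = 0.467, 0.66/1.183 = 0.558, 0.66/1 = 0.66; power 51 / 66 / 80%.
- Drift 0.3 then 0: D shift = (0.66 − 0.30) / SD of D = 0.255 / 0.304 / 0.360; power 19 / 25 / 33%, against 80% for pre/post.

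**Precision.** The 95% CI half-width is 2.093/√20 = 0.47 SD for one week's change. For D it is 0.66 / 0.55 / 0.47 SD.

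**The case against.** **The plan does not say pre/post.** A reader might infer that a biased test has been specified. It has not: Section 10.0 leaves the contrast open, and the own-controls wording in Section 9.0 points towards using week 1. The time factor in the ANOVA could also be meant to cover all ten occasions. This limits the point to an unspecified contrast and the risk it carries. It does not remove the point, because a statement of design purpose is not a test, and no section states the comparison.

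**The drift is assumed.** This stands. A reader might infer from the repeated nerve stimulation while standing that drift is likely. The documents do not support that: long standing could tire participants rather than improve their scores, nothing links stimulus counts to range of motion, Ashworth or Fugl-Meyer scores, and the text does not say that the full battery is run at every time point. The inclusion requirement of neurological stability for more than 6 months also limits natural recovery.

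**D can be the worse test.** This stands too. Participants have five test exposures before week 2, so a practice plateau is plausible, and the tables show what D then costs. It is not safe to report D alone.

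**D does not isolate the needle.** This stands. The order is fixed and there is no sham. Section 9.0 also follows needling with repeated passive ankle movement and plantarflexor contractions that have no counterpart in the control week. D therefore estimates the effect of the whole DDN session, order and expectation included.

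**The reflex analysis matters more.** It carries Aims 1 and 2 and has the same gap, so it belongs in the same edit.

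**Conclusion.** The point holds in a limited form. The analysis text does not name the contrast for functional change, and no stated analysis, functional or reflex, uses the control week. If the functional test is run as DDN-week pre/post, it cannot separate DDN from change that occurs anyway. False-positive rates of 14% to 56% follow from assumed drifts of 0.2 to 0.5 SD and show sensitivity only. They do not forecast what will happen in this trial.

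D restores the 5% rate only if drift is equal in both weeks, and removes only drift common to both. Its advantage over pre/post reverses when DDN-week drift is below about 41% to 50% of control-week drift. That is why the remedy is to state D and show both weeks, not simply to replace one test with another. Because these are supportive measures in a pilot, the point is minor to moderate.

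**What to change.** In Section 10.0, replace the functional t-test clause with text to this effect:

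- For each functional outcome, the contrast is D = (post minus pre in the DDN week) minus (change to the matching time point in the control week), paired within participant.
- D = 0 is tested with a paired t-test at one post-DDN time point named in advance. The Modified Ashworth Scale, being ordinal, uses a signed-rank test.
- Each week's change is reported with its 95% CI beside D, so that unequal drift or a plateau is visible.
- These tests are exploratory, and D is described as the effect of the whole DDN session, including order and expectation.

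In the same edit, add week and the week-by-time comparison to the reflex analysis.

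No new visits, participants or data are needed, provided the control-week functional measurements follow the matched spacing; one sentence should confirm this. The cost is precision when r is below 0.5 (power 51% or 66% instead of 80% for 0.66 SD at r = 0 or 0.3), and bias against DDN if practice change flattens after week 1.

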11.0 Provisions to Monitor the Data to Ensure the Safety of Subjects

From the time of initial contact (before obtaining the informed consent for study participation) to the end of project (i.e., study publication), the confidentiality and rights of all the study participants and potential study candidates are protected. At the time of consent, the potential study candidate is assured that s/he has the right to stop participation in any or all parts of the study at any time with no penalty or loss of benefits to which s/he is otherwise entitled.

After the pre-screening, the clinical research coordinator will discard all records of potential study candidates who are not eligible to participate in the study. For candidates after stroke, after the medical/neurological screening (by the study therapist) and the EMG screening, all records of non-eligible candidates will be discarded. For the eligible participants, who will therefore go through the study protocol, the medical, neurological, and personal information will be securely stored in locked cabinets of a locked room and on MUSC's secure network storage, and only the principal and co-investigators and the research coordinator will have access to the participant's confidential information. For the length of the study, limited personal information (specifically, the participant's name, address, and social security number) will also be accessible to the program administrator for processing the participant reimbursement paperwork. Investigators and therapists, who run data collection sessions, will have access to the EMG and other collected data for the purpose of analysis, but will have no access to the participant's confidential information. Alphanumeric codes will be assigned to each participant's dataset to protect confidentiality.

At the time of obtaining consent, the potential participant will be made aware of the fact that

we cannot guarantee the protection of the confidentiality of his/her records, although every reasonable effort will be made to protect it. The consent form will clearly state as “*By law, representatives of the sponsoring organization or other regulatory authorities may inspect these records. All personal information made available for inspection will be handled in strictest confidence and in accordance with data protection laws.*”

The coordinator will check with each participant for any discomfort or adverse events that s/he might have experienced after each session. If and when adverse effects or events and any protocol deviations occur, the coordinator or the PI will immediately report them to the department and the IRB.

12.0 Withdrawal of Subjects

- Some of the participants may find DDN to be stressful or painful (e.g., in case of individuals with needle phobias), even after careful screening with the above listed inclusion/exclusion criteria. All participants are assured that they have the right to stop participation at any part of the study procedures.
- DDN is a commonly practiced therapeutic method to treat spasticity and pain in individuals with neurological and non-neurological (orthopedic) injuries. Careful screening with the above listed inclusion/exclusion criteria ensures safe administration of DDN.

13.0 Risks to Subjects

- There is a risk (1-10/100) of local bleeding, hematoma, and needling site pain. In order to minimize this risk, the patient will be placed in a recumbent or comfortable position for the technique and gentle massage/hemostasis will be applied to the needling site post needling [86].
- There is an uncommon risk (1-10/1000) of local or systemic infections or swelling. In order to minimize this risk a clean technique will be utilized with the use of gloves and cleaning the skin around the region with an alcohol swab pre needling [86].
- There is an uncommon risk (1-10/1000) for strong pain during the treatment, nerve irritation, nerve injury, headache, fatigue, vertigo, and nausea. In order to minimize this risk the patient will be placed in comfortable position and will be monitored throughout needling. At any point the subject can request that the needling be discontinued [86].
- There is a rare risk (1-10/10000) for redness, itching, sweating, blood pressure changes, unconsciousness, tachycardia, breathing difficulties, or vomiting. In order to minimize this risk the patient will be placed in comfortable position and will be monitored throughout needling. At any point the subject can request that the needling be discontinued [86].
- There is a very rare risk (<1/10000) for a broken needle. This risk will be minimized by using the appropriate needle and not inserting the needle to the handle of the needle [86].
- There is a very small possibility that the recording and stimulating electrodes will produce minor irritations, such as itchiness. This is extremely unlikely, since the electrodes we use are designed for sleep studies (Vermed., Inc). If itchiness does occur after the experiment, an over-the-counter topical steroid cream will be applied to the skin over which the electrodes were placed. Electrical stimulation of sensory or motor nerves may generate brief non-painful sensations. Careful adjustment of the stimulus intensity and electrode placement should minimize any discomfort.

- There is a risk of loss of confidentiality. From the time of initial contact (before obtaining the informed consent) to the end of the study, every reasonable effort will be made to protect the confidentiality and rights of all the study participants and potential study candidates.
- There is a risk of falling when performing the 10 meter walk test. The participant can use an adaptive device during this assessment, and the risk of falling is no greater than when walking at home or in the community with the same device. The risk of falling will be minimized by study staff, who will walk beside the participant and assist if he/she becomes fatigued or experiences a loss of balance.
- The experimental procedures may have unknown side effects. The researchers will inform study participants if any new side effect is discovered.

